18.7 HIT-6 (week 4, 12, and 24)

The HIT-6 (v1.0) is a Likert-type, self-reporting questionnaire designed to assess the impact of an occurring headache and its effect on the ability to function normally in daily life.⁴ The HIT-6 contains 6 questions, each item is rated from “never” to “always” with the following response scores: never = 6, rarely = 8, sometimes = 10, very often = 11, and always = 13. The total score for the HIT-6 will be sum of each item score which ranges from 36 to 78.⁵ The life impact derived from the total score is described as followed: Severe (≥ 60), Substantial (56-59), Some (50-55), Little to None (≤ 49).

The HIT-6 will be reported monthly and missing values will be imputed using multiple imputation methods based on the amount and pattern of missing data.

18.8 MIDAS (weeks 12 and 24)

The MIDAS Questionnaire was developed to assess headache-related disability.⁶ It is a 5-item instrument which assigns a disability score to patients based on the number of days in the past 3 months that patients report activity limitations due to migraine. The MIDAS score will be the sum of days reported from questions 1 through 5.⁷

The MIDAS score may be categorized according to the following:⁷

Score	Grade	Disability
0-5	I	Little or no disability
6-10	II	Mild disability
11-20	III	Moderate disability
≥ 21	IV	Severe disability

The MIDAS will be reported quarterly (weeks 12 and 24), and missing values will be imputed using multiple imputation methods based on the amount and pattern of missing data.

18.9 Drug Switching

Drug switching will be based on monthly follow-up visits. In the case in which follow-up data is missing and it is unknown whether the patient received their treatment or switched, we will assume that the patient is still receiving their index therapy.

18.10 TSQM (week 24)

The TSQM (version 1.4) measures the satisfaction of patients with their treatment with respect to side effects, effectiveness, convenience, and global satisfaction.⁸ The TSQM score ranges from 0 to 100 with high scores indicating greater satisfaction for each domain. Scores will for each domain will be calculated according to the following:

Effectiveness: $([(Item\ 1 + Item\ 2 + Item\ 3) - 3] \div 18) \times 100$ If one item is missing:
 $([(Sum\ of\ Item\ 1? + Item\ 2? + Item\ 3?)) - 2] \div (12) \times 100$

Side effects: $([(Sum\ of\ Item\ 5\ to\ Item\ 8) - 4] \div 16) \times 100$ If one item is missing:
 $([(Sum\ of\ Item\ 5? \ to\ Item\ 8?)) - 3] \div (12) \times 100$

Convenience: $([(Sum\ of\ Item\ 9\ to\ Item\ 11) - 3] \div 18) \times 100$ If one item is missing:
 $([(Sum\ of\ Item9? \ to\ Item11?)) - 2] \div (12) \times 100$

Overall satisfaction, first recode Item14_recode = $(Item14 - 1) \times 5/6$, then: $([(Sum\ of\ Item\ 12\ to\ Item\ 14) - 3] \div (12) \times 100$ If any one Item is missing: $([(Sum\ of\ Item\ 12? \ to\ Item\ 14?)) - 2] \div (8) \times 100$

The TSQM will be reported at week 24, and missing values will not be imputed.

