## Appendix XIII

### Treatment Satisfaction Questionnaire for Medication (TSQM)

#### TSQM (Version 1.4)

##### Treatment Satisfaction Questionnaire for Medication

**Instructions:** Please take some time to think about your level of satisfaction or dissatisfaction with the medication you are taking in this clinical trial. We are interested in your evaluation of the effectiveness, side effects, and convenience of the medication *over the last two to three weeks, or since you last used it*. For each question, please place a single check mark next to the response that most closely corresponds to your own experiences.

1. How satisfied or dissatisfied are you with the ability of the medication to prevent or treat your condition?

- 1 Extremely Dissatisfied
- 2 Very Dissatisfied
- 3 Dissatisfied
- 4 Somewhat Satisfied
- 5 Satisfied
- 6 Very Satisfied
- 7 Extremely Satisfied

2. How satisfied or dissatisfied are you with the way the medication relieves your symptoms?

- 1 Extremely Dissatisfied
- 2 Very Dissatisfied
- 3 Dissatisfied
- 4 Somewhat Satisfied
- 5 Satisfied
- 6 Very Satisfied
- 7 Extremely Satisfied

3. How satisfied or dissatisfied are you with the amount of time it takes the medication to start working?

- 1 Extremely Dissatisfied
- 2 Very Dissatisfied
- 3 Dissatisfied
- 4 Somewhat Satisfied
- 5 Satisfied
- 6 Very Satisfied
- 7 Extremely Satisfied

4. As a result of taking this medication, do you experience any side effects at all?

- 1 Yes
- 0 No (if No, then please skip to Question 9)

5. How bothersome are the side effects of the medication you take to treat your condition?

- 1 Extremely Bothersome
- 2 Very Bothersome
- 3 Somewhat Bothersome
- 4 A Little Bothersome
- 5 Not at All Bothersome

6. To what extent do the side effects interfere with your physical health and ability to function (i.e., strength, energy levels, etc.)?

- 1 A Great Deal
- 2 Quite a Bit
- 3 Somewhat
- 4 Minimally
- 5 Not at All

7. To what extent do the side effects interfere with your mental function (i.e., ability to think clearly, stay awake, etc.)?

- 1 A Great Deal
- 2 Quite a Bit
- 3 Somewhat
- 4 Minimally
- 5 Not at All

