8. To what degree have medication side effects affected your overall satisfaction with the medication?

- 1 A Great Deal
- 2 Quite a Bit
- 3 Somewhat
- 4 Minimally
- 5 Not at All

9. How easy or difficult is it to use the medication in its current form?

- 1 Extremely Difficult
- 2 Very Difficult
- 3 Difficult
- 4 Somewhat Easy
- 5 Easy
- 6 Very Easy
- 7 Extremely Easy

10. How easy or difficult is it to plan when you will use the medication each time?

- 1 Extremely Difficult
- 2 Very Difficult
- 3 Difficult
- 4 Somewhat Easy
- 5 Easy
- 6 Very Easy
- 7 Extremely Easy

11. How convenient or inconvenient is it to take the medication as instructed?

- 1 Extremely Inconvenient
- 2 Very Inconvenient
- 3 Inconvenient
- 4 Somewhat Convenient
- 5 Convenient
- 6 Very Convenient
- 7 Extremely Convenient

12. Overall, how confident are you that taking this medication is a good thing for you?

- 1 Not at All Confident
- 2 A Little Confident
- 3 Somewhat Confident
- 4 Very Confident
- 5 Extremely Confident

13. How certain are you that the good things about your medication outweigh the bad things?

- 1 Not at All Certain
- 2 A Little Certain
- 3 Somewhat Certain
- 4 Very Certain
- 5 Extremely Certain

14. Taking all things into account, how satisfied or dissatisfied are you with this medication?

- 1 Extremely Dissatisfied
- 2 Very Dissatisfied
- 3 Dissatisfied
- 4 Somewhat Satisfied
- 5 Satisfied
- 6 Very Satisfied
- 7 Extremely Satisfied

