11.2 Analysis Methodology for the Exploratory Endpoints

11.2.1 Estimand for the Number of Good Days (Week 1-4, 1-12, and 1-24) and Exploratory Endpoints

A summary of the intercurrent events that will be addressed and the estimand attributes can be found below.

The estimand is the difference in the mean weekly number of good days within each specified time interval between eptinezumab compared to other advanced preventive therapies (erenumab, fremanezumab, galcanezumab, or onabotulinumtoxinA) in adults with migraine on concomitant acute migraine therapy who have failed ≥ 2 prior oral preventive therapies and who are naïve to advanced migraine therapy based on a treatment policy strategy in which patients are analyzed according to the randomized group and are included in the analysis regardless of discontinuation or switching of the index migraine therapy during the follow-up period.

Intercurrent events that will be addressed include:

- Discontinuing the index preventive migraine medication with or without initiation of a new preventive therapy (i.e., a treatment switch).
- Withdrawal from the study due to lack of efficacy, adverse event, participant request, physician request, or loss to follow-up.
- Interruption or termination of infusions.

Attributes of the estimand for the number of good days include:

- The index treatment of interest is eptinezumab (100 mg or 300 mg) compared to other advanced preventive therapies (erenumab 70 mg or 140 mg, fremanezumab 225 mg or 675 mg, galcanezumab 120 mg, and onabotulinumtoxinA 155 units)
- The population is all patients with migraine who fulfil the inclusion and exclusion criteria.
- The primary endpoint of interest is the mean number of good days across weeks 1-12 after randomization
- The population-level summary is the mean difference between eptinezumab and other advanced preventive therapies for the endpoint

Estimands for the remaining exploratory endpoints can be formulated similarly to the estimand for the number of good days described above.

EQ-5D (weeks 1-4, 1-12, and 1-24)

- The endpoint to be obtained is the weekly EQ-5D score in each specified time interval
- The population level summary is the difference in mean weekly EQ-5D score in patients on eptinezumab relative to advanced migraine therapies in each time interval

PI-MBS (weeks 1-4, 1-12, and 1-24)

- The endpoint to be obtained is the weekly most bothersome symptom and associated severity

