The difference in mean TSQM score for each domain (effectiveness, side effects, convenience, and overall satisfaction) at week 24 will be estimated using an ordinary least

square model. Independent variables will include a treatment indicator (eptinezumab vs other advanced therapies) and a vector of covariates identified to be significantly different between treatment groups after randomization. The hypothesis tested will be that the treatment term is significantly different from zero using a two-sided test at $p<0.05$. The population level summary will be the difference in mean TSQM score at week 24.

Index drug switching (weeks 1-12, and 1-24)

The difference in the odds of index drug switching will be estimated using a logistic regression model. Independent variables will include a treatment indicator (eptinezumab vs other advanced therapies) and a vector of covariates identified to be significantly different between treatment groups after randomization. The hypothesis tested will be that the treatment term is significantly different from zero using a two-sided test at $p<0.05$. The population level summary will be the odds ratio of index drug switching in the eptinezumab group relative to other advanced therapies. The analysis will be conducted weeks 12 and 24.

SDMQ-9 (screening and week 24)

The average SDMQ-9 score will be calculated for each treatment group and descriptively compared at screening and week 24.

SURE score at screening

The average SURE score will be calculated for each treatment group and descriptively compared at screening.

PAM-10 score (screening, week 12 and 24)

The average PAM-10 score will be calculated for each treatment group and descriptively compared at screening, week 12, and week 24.

ISS score (screening, week 12 and 24)

The ISS score or item responses will be analyzed descriptively using averages and proportions in the eptinezumab group at screening, week 12, and week 24.

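### TSQM scoring in SAP 18.10: the overall-satisfaction formula misses the stated 0–100 range, and, separately, the side-effects score has no rule for participants who answer No to item 4

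*SAP*

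**What the plan says.** SAP 18.10 gives a scoring formula for each of the four TSQM domains and states that "The TSQM score ranges from 0 to 100 with high scores indicating greater satisfaction for each domain".

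For the fourth domain the text begins "Overall satisfaction, first recode Item14_recode" and sets the recode to (Item 14 − 1) × 5/6. It then sums items 12 to 14, subtracts 3 and divides by 12. If one item is missing it subtracts 2 and divides by 8. The sum names Item 14, not the recoded variable. In Protocol Appendix XIII, items 12 and 13 are coded 1–5, and item 14 ("Taking all things into account, how satisfied or dissatisfied are you with this medication") is coded 1–7.

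For side effects, 18.10 sums items 5 to 8, subtracts 4 and divides by 16, with a version for one missing item. In Appendix XIII, item 4 asks whether there are any side effects at all, and the negative answer reads "No (if No, then please skip to Question 9", so items 5–8 are then blank by design. Section 18.10 does not mention item 4. It closes with "The TSQM will be reported at week 24, and missing values will not be imputed".

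SAP 11.2.2 tests every domain between groups at p<0.05 by ordinary least squares: "The difference in mean TSQM score for each domain (effectiveness, side effects, convenience, and overall satisfaction) at week 24 will be estimated". On who should be compared, SAP 11.2.1 says "The population is all patients with migraine who fulfil the inclusion and exclusion criteria" and adds "Estimands for the remaining exploratory endpoints can be formulated similarly to the estimand for the number of good days described above".

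**The concern.** There are two defects of different kinds.

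The first is arithmetic. A recode to 0–5 cannot be combined with an offset and divisor built for 1–5 and still give 0–100. Some scores fall outside the stated range, and a participant's score depends on which item is left blank. Two programmers could also produce different scores, because the sum does not say which item-14 variable it uses.

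The second is a missing rule. If No at item 4 leaves the score undefined, participants without side effects drop out of the side-effects comparison. Those who remain were selected by something that happened after randomisation and that treatment may influence. Randomisation no longer protects that contrast, and it is not the contrast that 11.2.1 describes. The study is open-label, so a scoring rule left open could be settled after results are known.

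**Working it through.** **Inputs.** Item codings come from Protocol Appendix XIII: items 1–3, 9–11 and 14 are 1–7; items 5–8, 12 and 13 are 1–5. Formulas come from SAP 18.10. Every permitted response pattern was enumerated.

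**Reproducing 0–100 where the plan succeeds.**
- Effectiveness and convenience: (3 − 3)/18 = 0 and (21 − 3)/18 × 100 = 100. With one item missing: (2 − 2)/12 = 0 and (14 − 2)/12 × 100 = 100.
- Side effects, items 5–8 answered: (4 − 4)/16 = 0 and (20 − 4)/16 × 100 = 100. With one missing: (3 − 3)/12 = 0 and (15 − 3)/12 × 100 = 100.

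**Overall satisfaction.** The recode maps 1–7 to 0–5.
- Minimum: (1 + 1 + 0 − 3)/12 × 100 = −8.33. Maximum: (5 + 5 + 5 − 3)/12 × 100 = 100.
- Item 12 or 13 missing: (1 + 0 − 2)/8 × 100 = −12.5, up to (5 + 5 − 2)/8 × 100 = 100.
- Item 14 missing: (1 + 1 − 2)/8 = 0, up to 100.

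| Reading | Complete (175 patterns) | Item 12 or 13 missing (35 patterns) |
|---|---|---|
| Recoded item 14, as written | −8.33 to 100; 2 negative | −12.5 to 100; 2 negative |
| Raw item 14, same constants | 0 to 116.67; 4 above 100 | 0 to 125; 3 above 100 |
| 1 + (Item 14 − 1) × 4/6, with −3 and /12 (missing: −2, /8) | 0 to 100 | 0 to 100 |
| 0–5 recode, with −2 and /13 (missing: −1, /9) | 0 to 100 | 0 to 100 |
| Raw item 14, with −3 and /14 (missing: −2, /10) | 0 to 100 | 0 to 100 |

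The two negative complete patterns for items 12, 13 and 14 are (1,1,1) at −8.33 and (1,1,2) at −1.39. The lowest possible responder scores −8.33 if complete, −12.5 with item 12 or 13 blank, and 0 with item 14 blank.

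**Effect on the arm difference.** One unit of item 14 is worth (5/6)/12 × 100 = 6.94 points as written. It is worth (4/6)/12 × 100 = 5.56 under the 1–5 recode, (5/6)/13 × 100 = 6.41 under the /13 version and 100/14 = 7.14 under raw /14. Over the 175 patterns, weighted equally, the printed score correlates 0.994 with the 1–5 version and 0.996 with the raw /14 version.

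**Side effects.** No at item 4 leaves four items blank. The formula tolerates one and nothing is imputed, so no score results. Let p be the proportion reporting side effects in an arm and m the mean score among them.
- Reporters only: the arm difference is the difference in m. With equal m it is 0, whatever the gap in p.
- Scoring No as 100: the arm mean is 100 − p(100 − m). With equal m the difference is (gap in p) × (100 − m). For assumed gaps of 5 to 30 percentage points and m of 25 to 75, this runs from 0.05 × 25 = 1.25 to 0.30 × 75 = 22.5 points.

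Scoring No as 100 has a cost. At assumed rates of 10% to 60%, at least 90% to 40% of participants sit at exactly 100. The variance is p × SD² + p(1 − p)(100 − m)². With m = 50 and SD = 20 (assumed):

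| p | Overall SD | Skewness | Detectable difference among affected: reporters only | Same, all participants with No = 100 |
|---|---|---|---|---|
| 10% | 16.3 | −3.34 | 26.5 | 64.8 |
| 30% | 25.4 | −1.41 | not computed | not computed |
| 60% | 29.0 | −0.35 | 10.3 | 19.2 |

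Detectable differences are for 80% power, two-sided alpha 0.05 and 100 per arm, with equal p in both arms. Over m of 25–75, SD of 15–25 and p of 10–60%, the all-participant figure is 1.2 to 4.6 times the reporters-only figure.

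**The case against.** The overall-satisfaction error is close to cosmetic. If the intended score is the 0–5 recode with −2 and /13, the printed complete-response score is a straight-line transformation of it: p-values are unchanged and differences shrink by 12/13. This stands for complete responses. It does not make the printed range right, and it fails where item 12 or 13 is missing, because the constants then change.

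On side effects, 18.10 is silent. It does not state an exclusion. A designed skip is not clearly a missing value, and scoring it is not clearly imputation, so the no-imputation sentence does not forbid a rule. That is fair, but no section supplies one.

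The TSQM asks about the last two to three weeks or since last use, so it does not measure side-effect frequency over the trial; the adverse event tables in SAP 12 do that. SAP 5 summarises all assessment data, so a percentage for item 4 may appear anyway. Both points limit the loss. Neither changes who enters the test, and SAP 12 groups events by therapy received. Since the first dose must be the randomised drug (Protocol 6.3.1), that grouping matches randomisation only until participants switch.

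A reader might infer that both domains break the 0–100 range. They do not: the side-effects range is correct once items 5–8 are answered. A reader might also infer that a difference in side-effect rates can never show in the test. That follows only if affected participants average the same in both arms. If the extra side effects in one arm are milder or worse, the means differ and the test moves.

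**Conclusion.** Both defects hold, as separate points. The overall-satisfaction formula is wrong as written: it gives −8.33 to 100 (−12.5 to 100 with item 12 or 13 missing), and summing raw item 14 does not rescue it. These figures are exact, and the effect on the arm difference is small. The side-effects formula is arithmetically sound but lacks a rule for No at item 4. Taken as written, its test compares a post-randomisation subset, contrary to the all-patient estimand.

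The side-effects sizes are illustrative. The documents give no rates, means or SDs, and the 1.25 to 22.5 points also depend on scoring No as 100, which neither document states. The scale is two of the four TSQM domains, one of twelve exploratory endpoints in SAP Panel 1, in a study whose objectives are all exploratory (Protocol 3.3). It should be corrected before analysis but does not threaten the study as a whole.

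**What to change.** **Overall satisfaction (18.10).** Choose one internally consistent version, checked against the instrument's scoring manual:
- 1 + (Item 14 − 1) × 4/6, with −3 and /12; one item missing: −2 and /8.
- The existing 0–5 recode, with −2 and /13; item 12 or 13 missing: −1 and /9; item 14 missing: −2 and /8.
- Raw item 14, with −3 and /14; item 12 or 13 missing: −2 and /10; item 14 missing: −2 and /8.

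Name the item-14 variable in both the complete and the one-missing formula.

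**Side effects (18.10).** Add a rule keyed on item 4, by one of two routes:
- Score No as 100, the formula's best value, subject to the scoring manual. This matches the all-patient estimand. It brings a ceiling spike and less sensitivity to severity among affected participants, so revise the normality rationale in 11.2.4 for this domain, for example with robust standard errors.
- Keep the analysis among reporters and label it a conditional, non-randomised comparison.

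Under either route, set the score to missing when item 4 is blank and items 5–8 are unanswered, and when item 4 is Yes and two or more of items 5–8 are blank. Report the percentage answering Yes to item 4 by randomised arm.

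**Cost.** Two scoring rules in 18.10, one sentence in 11.2.4 if No scores 100 (otherwise a label), and one row in the TSQM table. Item 4 is already collected.

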18.11 SDMQ-9 (screening and week 24)

The SDM-Q-9 measures the extent to which patients are involved in the process of decision-making from the perspective of the patient.⁹ The questionnaire contains nine items, each describing one step of the SDM process. It was developed to assess the degree to which patients feel involved in the decision-making process. The items are scored from 0 to 5 on a six-point Likert scale ranging from "completely disagree" (0) to "completely agree" (5).¹⁰ Scores will be summed across the 9 items to calculate the raw total score ranging from 0 to 45 with higher scores indicating higher shared decision making.

The SDMQ-9 will be reported at screening and week 24, and missing values will not be imputed.

18.12 SURE (screening)

The SURE test is a brief 4-item screening questionnaire the patient uses to assess their readiness and capacity to decide or to determine whether they are comfortable with their decision.¹¹ An answer of "yes" to an item yields a value of 1 and an answer of "no" yields a value of 0. Item values are summed to calculate the total score. A score of 4 indicates that a patient should not be experiencing a clinically significant decisional conflict, whereas a value of <4 indicates the presence of a clinically significant decisional conflict.

The SURE score will be reported at screening, and missing values will not be imputed.

18.13 PAM-10 (screening, week 12 and 24)

The Patient Activation Measure evaluates the knowledge, skills, and confidence a patient has in managing his or her health conditions.¹² In this study the 10-item Patient Activation Measure (PAM) tool will be utilized. PAM-10 uses a four-point Likert scale of agreement-disagreement to respond to each item. PAM is scored on a scale from 0 to 100 from which four levels of activation have been identified: Level 1 (0.0–47.0) low activation suggesting

that the person does not yet understand their role in healthcare to Level 4 (72.5–100) indicating that the person is proactive and engaged in recommended health behaviors and management of health conditions.¹³ Scores will be calculated based on item responses using a propriety algorithm.

The PAM-10 score will be reported at screening, week 12, and week 24, and missing values will not be imputed.

18.14 PSS

The Perceived Stress Scale (PSS) is a classic stress assessment instrument. The tool, measures how different situations affect feelings and perceived stress. The questions ask about feelings and thoughts during the last month.¹⁴ The 10 items use a 5-point Likert scale ranging from 0 (never) to 4 (very often). Item scores are summed to arrive at a total score ranging from 0 to 40, with higher scores indicating greater perceived stress.

The PSS will be reported monthly, and missing values will be imputed using multiple imputation based on the amount and pattern of missing data.

18.15 ISS (screening, week 12 and 24)

All participants receiving eptinezumab (regardless of initial treatment assignment) will complete an eptinezumab-specific survey describing their satisfaction with the infusion experience after each infusion while on site using a paper questionnaire.

The ISS item responses will be reported at screening, week 12, and week 24, and missing values will not be imputed.

